**11.2 Source Documents**

Source documents are defined as the results of original observations and activities of a clinical investigation. Source documents will include, but are not limited to, progress notes and screening logs. All source documents pertaining to this study will be maintained by the investigators and

**Protocol No: PRG-NY-15-013**

made available for inspection by authorized persons. The original signed informed consent form for each participating subject shall be filed with records kept by the investigators and a copy given to the subject.

**11.3 File Management at the Study Site**

It is the responsibility of the investigator to ensure that the study center file is maintained in accordance with Section 8 of the International Conference on Harmonization (ICH) Guideline for Good Clinical Practices (GCP).

**11.4 Records Retention at the Study Site**

FDA regulations require all investigators participating in clinical drug studies to maintain detailed clinical data for one of the following periods:

- a) A period of at least two years following the date on which a New Drug Application is approved by the FDA;
- b) A period of two years after Perrigo notifies the investigator that no further application is to be filed with the FDA.

The investigator must not dispose of any records relevant to this study without either (1) written permission from Perrigo or (2) providing an opportunity for Perrigo to collect such records. The investigator shall take responsibility for maintaining adequate and accurate electronic or hard copy source documents of all observations and data generated during this study. Such documentation is subject to inspection by Perrigo and the FDA.

**12. QUALITY CONTROL AND QUALITY ASSURANCE**

**12.1 Monitoring**

Perrigo has ethical, legal and scientific obligations to carefully follow this study in a detailed and orderly manner in accordance with established research principles and FDA regulations. All medical records (source documents) of the subjects participating in this study must be presented for review and verification of eCRFs.

**12.2 Auditing**

Perrigo (or representative) may conduct audits at the study center(s). Audits will include, but are not be limited to, drug supply, presence of required documents, the informed consent process, and comparison of eCRFs with source documents. The investigator agrees to participate with audits conducted at a reasonable time in a reasonable manner.

Regulatory authorities worldwide may also audit the investigator during or after the study. The investigator should contact Perrigo immediately if notified of such an audit, and must fully cooperate with the audits conducted at a reasonable time in a reasonable manner.

**13. ETHICS AND RESPONSIBILITY**

**Protocol No: PRG-NY-15-013**

This study must be conducted in compliance with the protocol, the United States Food and Drug Administration (FDA) regulations, any other countries regulations, and ICH GCP Guidelines.

**14. USE OF INFORMATION AND PUBLICATION**

All information supplied by Perrigo in connection with this study and not previously published, is considered confidential information. This information includes, but is not limited to, data, materials (i.e. the clinical protocol, eCRFs), equipment, experience (whether of a scientific, technical, engineering, operational, or commercial nature), designs, specifications, know how, product uses, processes, formulae, costs, financial data, marketing plans and direct selling systems, customer lists and technical and commercial information relating to customers or business projections used by Perrigo in its business. Any data, inventions, or discoveries collected or developed, as a result of this study is considered confidential. This confidential information shall remain the sole property of Perrigo, shall not be disclosed to any unauthorized person or used in any unauthorized manner without written consent of Perrigo, and shall not be used except in the performance of the study. As such, confidential study related information should not be included on the curriculum vitae of any participating investigator or study staff.

The information developed during the course of this clinical study is also considered confidential, and will be used by Perrigo in connection with the development of the drug. The information may be disclosed as deemed necessary by Perrigo to allow the use of the information derived from this clinical study, the investigator is obliged to provide Perrigo with complete test results and all data developed in the study. The information obtained during this study may be made available to other investigators who are conducting similar studies.

The investigator shall not make any publication related to this study without the express written permission of Perrigo.

[REDACTED]

[REDACTED]

15.3 APPENDIX C: [REDACTED]

[REDACTED]

To compare the safety and efficacy profiles of Perrigo UK FINCO's Ivermectin Cream, 1%, to Galderma Laboratories Soolantra® (Ivermectin) Cream, 1%, and to demonstrate the superior efficacy of the two active formulations over that of the vehicle in the treatment of Inflammatory Lesions of Rosacea.

3 Study Design and Sample Size

3.1 Study Design

For the purpose of exploring the above objectives, the study will be conducted as a double-blind, randomized, parallel-group, vehicle-controlled, multicenter trial.

Each subject will be randomly assigned to one of the following treatment groups [REDACTED]:

- (1) Test: Ivermectin Cream, 1%, [REDACTED]
- (2) Reference: Soolantra® Cream 1% (Ivermectin Cream 1%), Galderma Laboratories
- (3) Vehicle of test product, [REDACTED]

Subjects will be admitted into the study only after written informed consent has been obtained and all of the inclusion and none of the exclusion criteria have been met. Randomization will be performed according to a computer generated randomization scheme where the treatment group designation has been assigned to the subject number. The treatment designation will remain blinded until after the final database is locked. An independent third party will generate and hold the randomization code throughout the study. Randomized subjects will apply [REDACTED] the assigned study medication topically [REDACTED] onto each area of the face (chin, left cheek, right cheek, nose, and forehead), avoiding contact with the eyes (upper and lower eyelids), lips and nostrils once daily [REDACTED] prior to bedtime (approximately the same time) for 12 weeks.

Subjects will come to the study site for clinical evaluations at Visit 1/Day 1 (Baseline), Visit 2/Interim (Day 28 ±4 days), Visit 3/Interim (Day 56 ±4 days), and Visit 4//End of Study (Day 84 ±4 days) or at early discontinuation. Safety will be assessed by monitoring adverse events at each visit and at the Week 2/Day 14 (±4 days) Telephone Contact.

3.2 Sample Size

_____ subjects will be randomized _____ (Test:Reference:Vehicle) to obtain _____ mITT subjects and _____ PP subjects. _____

4 Populations To Be Analyzed

Three subject populations are defined as follows:

- (1) Intent-to-treat (ITT) population: any subject that was randomized, received and used study medication;
- (2) Modified Intent-to-treat (mITT) population: any subject, who met the inclusion/exclusion criteria, was randomized, received and used the study medication, and returned for at least one post-baseline efficacy assessment;
- (3) Per Protocol (PP) population: any subject who (a) met all inclusion/exclusion criteria; (b) was randomized and received and used study medication; (c) met the protocol criteria for compliance _____; (d) completed Visit 4/Week 12/Day 84 (End of Treatment/Early Termination Visit) within window OR was dropped from the study due to treatment failure and; (e) Without significant protocol violations that could have interfered with the administration of the treatment or the precise evaluation of treatment efficacy.

- [REDACTED]

[REDACTED]

[REDACTED]

[REDACTED]

5 Planned Analyses

5.1 Methodological Considerations

The study will be conducted under the same protocol across all the sites. No formal statistical analyses are planned to evaluate the consistency of efficacy results across the multiple clinical sites. These results, however, will be tabulated and if a site's efficacy data are obviously inconsistent with the results across all sites, this will be explored and addressed in the final study report.

All randomized subjects who received study medication will be evaluated for safety. The efficacy analysis will be conducted on both the PP and the mITT populations.

Two-sided hypothesis testing will be conducted for all the tests. Resulting p-values less than 0.05 will be considered statistically significant unless noted otherwise. No adjustments of p-values for multiple comparisons will be made. No interim analyses are planned.

SAS software will be used for all data analyses and tabulations.

5.2 Handling of Dropouts or Missing Data

[REDACTED]

[REDACTED]

5.3 Demographics and Baseline Characteristics

Baseline variables (e.g., sex, age, ethnic origin) will be evaluated, adjusting for site, to identify differences between treatment groups, which were not eliminated by randomization. Any significant baseline differences will be reviewed for their potential impact on the efficacy findings.

Continuous variables at baseline will be examined by two-way analysis of variance (ANOVA) with treatment and site as fixed effects when normal error and homogeneous variance assumptions are satisfied, or by the nonparametric rank based ANOVA when they are not, to compare treatment group differences.

Categorical variables such as gender, race, etc., will be examined by Cochran-Mantel-Haenszel test, stratified by site. Summary tables by treatment group will be presented. For each continuous variable, the summary will include the mean, standard deviation, minimum and maximum. For each categorical variable, the summary will include frequencies and percentages.

5.4 Subject Accountability

A summary of subject disposition will be provided for all subjects. Descriptive summaries of subject disposition, reason for discontinuation, and analyses population will be provided by treatment group. The data will also be presented in subject data listings.

5.5 Efficacy Variables and Analyses

5.5.1 Primary Endpoint

The primary efficacy endpoint of the study is the mean percent change from baseline to Visit 4/Week 12 in the inflammatory (papules and pustules) lesion counts.

Equivalent Efficacy

For the mean percent change from baseline in the inflammatory lesion counts, the Test treatment will be considered to be therapeutically equivalent to the Reference treatment if the 90% confidence interval on the Test-to-Reference ratio of means, calculated by Fieller's Method, falls within the interval 0.80 to 1.25. The compound hypothesis to be tested for therapeutic equivalence between test and reference is:

$$H_0: \mu_T/\mu_R \leq 0.80 \text{ or } \mu_T/\mu_R \geq 1.25 \text{ versus}$$

$$H_A: 0.80 < \mu_T/\mu_R < 1.25.$$

Where μ_T and μ_R are the mean percent change from baseline to Visit 4/Week 12 (Day 84) in inflammatory lesions counts for the test treatment and the reference treatments, respectively. The null hypothesis is rejected when the two-sided 90% confidence interval (CI) for the ratio of means between test and reference products is between 0.80 and 1.25. Rejection of the null hypothesis supports the conclusion of therapeutic equivalence between test and reference products for the primary efficacy variable.

The two-sided 90% confidence interval will be constructed using an ANOVA model adjusting for the effects of treatment and site. [REDACTED]

The therapeutic equivalence evaluation in the per-protocol (PP) population will be considered definitive and that in the mITT will be considered supportive.

Analysis for therapeutic equivalence will be performed based on the following SAS code (SAS Institute v.9.1.3):

The key procedure used to determine CIs for ratio of treatment means:

```
PROC GLM DATA=inf_pp;
  CLASS trt invid;
  MODEL pchg_inf = trt invid;
  ESTIMATE 'ratio=c' intercept (1-c) trt 1 -c;
RUN;
```

Where the ESTIMATE statement is run to locate the c value (our Test/RLD) for the 90% CI.

Superiority

For the percent change from baseline in the inflammatory lesion counts, each active treatment will be evaluated to determine if it has superior efficacy to that of the Vehicle at Visit 4/Week 12 (Day 84) via an ANOVA model containing terms for treatment and site. The compound hypothesis to be tested for superiority of test and reference over Vehicle is:

$$H_0 : \mu_T \leq \mu_V \text{ or } \mu_R \leq \mu_V \text{ versus}$$

$$H_A : \mu_T > \mu_V \text{ and } \mu_R > \mu_V$$

Where μ_T , μ_R and μ_V are the mean percent change from baseline to Visit 4/Week 12 (Day 84) in inflammatory lesions counts for the test, the reference and the vehicle treatments, respectively. The null hypothesis is rejected when both p-values from the ANOVA are less than 0.05 (two-sided test). Rejection of the null hypothesis supports the conclusion of superiority of test and reference products over the vehicle product for the primary efficacy variable.

A skewness test (SAS® PROC UNIVARIATE) will be performed using the residuals from the ANOVA of the primary efficacy variable. If the skewness statistic is greater than 2 or less than -2, the analysis will be performed on the ranked mean percent change from baseline to Visit 4/Week 12 (Day 84) in inflammatory lesion counts.

Superiority analyses in the mITT population will be considered definitive and those in the PP will be considered supportive.

Analysis for superiority will be performed based on the following SAS code (SAS Institute v.9.1.3):

The key procedure used to compare mean values of an active treatment arm to vehicle:

```
PROC GLM DATA=inf_pp;
  CLASS trt invid;
  MODEL pchg_inf = trt invid /ss3;
RUN;
```

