## 8. STATISTICAL ANALYSIS

The sections that follow highlight sample size determination and the planned analyses for this study. A statistical analysis plan (SAP) will be prepared separately from this protocol which gives descriptions of the statistical methods, models, hypotheses and subject populations to be analyzed. The SAP will be completed and approved before locking the database and unblinding the study and will serve as a companion to the protocol and the *de facto* documentation of the proposed statistical evaluation. The SAP will be completed and finalized prior to breaking the blind.

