##### Equivalent efficacy

For the mean percent reduction from baseline in the inflammatory lesion count, the Test treatment will be considered to be therapeutically equivalent to the Reference treatment if the 90% confidence interval on the Test to Reference ratio of means, calculated by Fieller's Method, falls within the interval 0.80 to 1.25. The treatment means and estimate of residual variance for the confidence interval calculation will come from an Analysis of Variance of the Test and Reference results using a statistical model containing terms for Treatment and Site.

For the proportion of subjects with clinical success, the Test treatment will be considered to be therapeutically equivalent to the Reference treatment if the 90% confidence interval on the difference between Test and the Reference proportions is contained within the interval -20% to +20%. The confidence interval will be constructed using Wald's method with Yates' continuity correction.

Therapeutic equivalence evaluations in the per protocol (PP) population will be considered definitive and those in the mITT will be considered supportive.

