##### Superiority

For the percent reductions from baseline in the inflammatory lesion count, each active treatment will be evaluated to determine if it has superior efficacy to that of the Vehicle at Visit 4/Week 12 via an Analysis of Variance using a statistical model containing terms for Treatment and Site.

[REDACTED]

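### Could SAP 5.5.1 let Vehicle data into the primary Fieller interval, which protocol 8.1.4 limits to Test and Reference?

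*SAP*

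**What the plan says.** Protocol 8.1.4 (Equivalent efficacy) specifies the data behind the Fieller interval. The treatment means and the "estimate of residual variance for the confidence interval calculation will come from an Analysis of Variance of the Test and Reference results", in a model with treatment and site. The Superiority paragraph of the same section tests each active against Vehicle "via an Analysis of Variance using a statistical model containing terms for Treatment and Site" and names no such limit, so the two-arm restriction belongs to equivalence.

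SAP 5.5.1 (Equivalent Efficacy) says: "The two-sided 90% confidence interval will be constructed using an ANOVA model adjusting for the effects of treatment and site". A redaction follows at once. The hypothesis above it involves only the Test and Reference means. The printed step opens with "PROC GLM DATA=inf_pp", has no WHERE statement, and solves for the limits with "ESTIMATE 'ratio=c' intercept (1-c) trt 1 -c".

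The superiority step in SAP 5.5.1 reads a data set of the same name. Its caption is "The key procedure used to compare mean values of an active treatment arm to vehicle", and the decision rule needs "both p-values from the ANOVA are less than 0.05 (two-sided test").

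Protocol 8 describes the SAP both as a companion to the protocol and as the de facto "documentation of the proposed statistical evaluation".

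**The concern.** The protocol ties the interval to two arms, and the visible SAP sentence keeps the model terms but not the arms. The code does not settle the matter: it prints no subsetting line and shares a data set name with the comparison against Vehicle. In SAP 5.5.2 the code for the secondary endpoint does print arm limits.

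A programmer who worked from the printed step alone, with one data set holding all three arms, would get a three-arm mean square error and site adjustment. The ESTIMATE statement would not reveal this, because its two treatment coefficients still target Test and Reference if the Vehicle coefficient is taken as zero.

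The stake is the width of the definitive per-protocol interval. A more variable Vehicle arm would widen it and cost some power. A less variable one would narrow it and push the false-equivalence rate above the nominal 5%.

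**Working it through.** **1. What the documents settle**

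| Point | Protocol 8.1.4 | SAP 5.5.1 (visible text) |
|---|---|---|
| Arms behind the interval | Test and Reference | Not stated; redaction follows |
| Model terms | Treatment, site | Treatment, site |
| Method and limits | Fieller, 90%, 0.80 to 1.25 | Same |
| Vehicle in the equivalence fit | No | Nowhere stated |

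The SAP is silent on the arms where the protocol is explicit. Silence is not a contradiction, and blacked-out text cannot be counted as absent.

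**2. What the code can show**

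- The name `inf_pp` cannot be literal throughout. It is also printed in the superiority step, where the mITT population is definitive.
- The superiority step has no contrast or least-squares-means statement. On three arms it would give one overall treatment test, not the two p-values that the rule needs. It gives those two only if run on one active-Vehicle pair at a time, which fits its caption. If the data set stands for a pair there, the natural pair in the equivalence step is Test and Reference.
- Two treatment coefficients suit a two-level factor. They do not prove one.
- Each step is introduced as the key procedure, so a subsetting step may lie outside the excerpt.
- The WHERE lines in SAP 5.5.2 are needed to form a two-by-two table. They do not imply that a step without one uses every arm.

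**3. Size if Vehicle were included anyway**

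There is no plan figure to reproduce: sample size, SDs and allocation are redacted (protocol 8.1.3, SAP 3.2). Every input below is an assumption.

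Let f be the arm shares and r the Vehicle-to-active SD ratio, with equal SDs in the two actives and site effects ignored. The three-arm fit multiplies the estimated standard error by

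m = sqrt(fT + fR + fV × r²).

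At a true ratio of 0.80 the large-sample false-equivalence rate is Φ(−1.645 × m), which does not contain N. For 2:2:1 and r = 0.8: m = sqrt(0.8 + 0.2 × 0.64) = sqrt(0.928) = 0.963, and Φ(−1.645 × 0.963) = 5.65%.

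| Allocation | r = 0.8 | r = 1 | r = 1.25 | r = 1.5 |
|---|---|---|---|---|
| 3:3:1 | 0.974; 5.46% | 1.000; 5.00% | 1.039; 4.37% | 1.086; 3.71% |
| 2:2:1 | 0.963; 5.65% | 1.000; 5.00% | 1.055; 4.14% | 1.118; 3.30% |
| 1:1:1 | 0.938; 6.14% | 1.000; 5.00% | 1.090; 3.65% | 1.190; 2.51% |

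(Half-width multiplier; false-equivalence rate.)

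Simulation at 2:2:1, r = 0.8 (400,000 draws, active SD 35, Reference mean 70, no site term) gives 5.64%, 5.64%, 5.67% and 5.65% with 120, 200, 300 and 400 per active arm. The two-arm error term gives 4.9% to 5.1% across the settings simulated.

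Power at a true ratio of 1 under the same assumptions:
- 120 per active arm: 92.3% falls to 90.7% (r = 1.25), and 92.2% falls to 88.5% (r = 1.5).
- 200 per active arm: 99.4% falls to 99.3% and 99.0%.
- 300 per active arm: no loss.

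**4. An example on the interval itself**

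Assume an observed mean reduction of 65 in both actives, SD 40 and 200 per active arm. Each mean has variance 40²/200 = 8. The two-arm interval is 0.903 to 1.107.

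- 100 Vehicle subjects, SD 30: pooled SD = sqrt((398 × 1600 + 99 × 900)/497) = 38.22; interval 0.908 to 1.102.
- 100 Vehicle subjects, SD 40: 0.903 to 1.107, unchanged.
- 100 Vehicle subjects, SD 60: pooled SD 44.70; interval 0.893 to 1.120.
- 200 Vehicle subjects, SD 60: pooled SD 47.61; interval 0.886 to 1.129.

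All of these lie inside 0.80 to 1.25.

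**The case for a change.** The best case for a change is that the SAP is the working record of the analysis and that programmers follow its code. The code block itself is not redacted and carries no arm limit. A three-arm run would produce a plausible ratio without any warning. Where Vehicle is less variable, the excess false-equivalence rate does not shrink as the trial grows. Writing the limit down takes one line before unblinding. The price in degrees of freedom is trivial: with 20 sites and 102/102/51 subjects, residual degrees of freedom are 183 instead of 233, and the t quantile rises by 0.11%.

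The factual part stands: the visible SAP text and printed step do not repeat the limit, and the arithmetic is right. What does not follow is that the plan lacks the rule. The protocol supplies it, and the redacted words or an unprinted data step may repeat it.

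The power figures also depend on the chosen inputs. With 200 per active arm, the assumptions in step 3 give a loss of 0.1 to 0.4 points. A separate simulation with SD 40, mean 65, 200 Vehicle subjects at SD 55 and 20 sites fell from about 95% to 91%. These figures describe a scenario that no visible text says will occur.

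**Conclusion.** No change to the plan follows. This is a detail that the SAP leaves to the protocol, and a competent analyst fills it correctly: protocol 8.1.4 names the arms, the SAP hypothesis concerns only those arms, and nothing visible points to a three-arm fit. An added line would only repeat a limit already stated.

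If the code were nevertheless run on all three arms, the effect would be practically nil at equal SDs. Over the assumed range (Vehicle-to-active SD ratio 0.8 to 1.5, allocation 3:3:1 to 1:1:1), the half-width would be multiplied by 0.938 to 1.190 and the false-equivalence rate would lie between 2.5% and 6.1%. Its direction cannot be known from the visible text. A routine programming check that the equivalence data set holds only Test and Reference subjects is sensible, but it is not an amendment.

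### Does the SAP's ESTIMATE statement fail to give the primary Test/Reference confidence interval because it lists no site coefficients?

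*SAP*

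**What the plan says.** SAP 5.5.1 (Equivalent Efficacy) declares equivalence on the primary endpoint if the 90% interval for the Test-to-Reference ratio of means, "calculated by Fieller's Method, falls within the interval 0.80 to 1.25". It adds: "The two-sided 90% confidence interval will be constructed using an ANOVA model adjusting for the effects of treatment and site". The sentence after that is redacted. The per-protocol result is definitive.

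The code is introduced with the words "The key procedure used to determine CIs for ratio of treatment means". It declares treatment and investigator (site) as CLASS effects, fits "MODEL pchg_inf = trt invid", and then gives "ESTIMATE 'ratio=c' intercept (1-c) trt 1 -c". The use of that line is explained as follows: "Where the ESTIMATE statement is run to locate the c value (our Test/RLD) for the 90% CI".

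Protocol 8.1.4 (Equivalent efficacy) takes the treatment means and the residual variance for the Fieller interval from an analysis of variance of the Test and Reference results, "using a statistical model containing terms for Treatment and Site".

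**The concern.** In a model with an intercept, treatment and site, every observation contributes 1 to the intercept, 1 to exactly one treatment and 1 to exactly one site. A linear function of the parameters is therefore estimable only if the intercept weight, the sum of the treatment weights and the sum of the site weights are equal. The printed line shows 1-c for the intercept, 1 and -c for treatment (sum 1-c), and nothing for site. Read with zeros for site, the three sums agree only when c = 1. The search for the confidence limits needs other values of c, above all the bounds 0.80 and 1.25.

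If that reading were right, the program for the definitive test of the trial's main claim would return no interval. Somebody would have to choose site weights afterwards. A worse reading is that the line gives the ratio at a single reference site. The equivalence verdict would then depend on which investigator is numbered last.

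**Working it through.** The sample-size text is redacted in both documents, so there is no stated figure to reproduce. The question is what coefficient vector the statement defines.

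**Step 1: zeros for site.** Take k = 20 sites (assumed).
- At c = 0.80 the weights are intercept 0.20, treatment 1 - 0.80 = 0.20, site 0.
- At c = 1.25 they are intercept -0.25, treatment 1 - 1.25 = -0.25, site 0.

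The site sum does not match, so the function is not estimable. In simulated unbalanced designs, the largest departure from the estimability condition L = L(X'X)⁻(X'X) was 0.005 to 0.029 at c = 0.80, 0.90, 1.10 and 1.25. At c = 1 it was about 1e-15. The algebra behind the concern is correct under its premise.

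**Step 2: what PROC GLM does.** When INTERCEPT appears in an ESTIMATE statement, GLM spreads its coefficient equally over CLASS effects that are not listed and not contained in a listed effect, as it does for least-squares means. Each site then gets (1-c)/k.
- With k = 20 this is 0.20/20 = 0.01 per site at c = 0.80, and -0.25/20 = -0.0125 at c = 1.25.
- The site weights now sum to 1-c, and the function is estimable at every c (departure about 1e-15).

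The vector is LSmean(Test) - c × LSmean(Reference). Writing (1-c)/k out explicitly for each site would produce the same vector.

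**Step 3: does the search return Fieller's interval?** The limits are the values of c at which

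(m_T - c·m_R) / √(V_TT - 2c·V_TR + c²·V_RR) = ± t(0.95, df).

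Squaring gives Fieller's quadratic

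(m_R² - t²V_RR)c² - 2(m_T·m_R - t²V_TR)c + (m_T² - t²V_TT) = 0.

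The assumed inputs were means 70 (Test), 69 (Reference) and 45 (Vehicle), SD 35, site SD 8 and unequal site sizes. One data set was simulated per design.

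| Arms | Sites | n | df | Ratio | c-search limits | Closed-form limits |
|---|---|---|---|---|---|---|
| 3 | 8 | 185 | 175 | 1.0117 | 0.8827 to 1.1603 | 0.8827 to 1.1603 |
| 3 | 20 | 326 | 304 | 0.9495 | 0.8559 to 1.0523 | 0.8559 to 1.0523 |
| 2 | 8 | 122 | 113 | 0.9468 | 0.8019 to 1.1164 | 0.8019 to 1.1164 |
| 2 | 20 | 296 | 275 | 0.9693 | 0.8814 to 1.0655 | 0.8814 to 1.0655 |

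**Step 4: the one-site reading.** This needs a reference-cell parameterisation in which the last site is absorbed into the intercept. The SAP code uses CLASS effects in PROC GLM and specifies no such thing. It would also contradict both texts, which ask for a ratio of treatment means. Its consequences would not be trivial. With a 7-point gap, the ratio is 58/65 = 0.89 at a Reference mean of 65, but 38/45 = 0.84 or 78/85 = 0.92 at a site averaging 45 or 85. These figures describe an analysis that the plan does not contain.

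**Step 5: how much site weighting matters.** With no interaction term, the Test minus Reference difference d is the same under any site weights. The ratio is 1 + d/m_R, so the weights act only through the level m_R. If d = 0, the estimated ratio is 1 whatever the weights. If d = -7, moving m_R from 65 to 66 takes the ratio from 58/65 = 0.892 to 59/66 = 0.894.

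Equal and size-proportional weights were compared in 2,000 simulated trials per scenario (assumed: 20 sites, Reference mean 65, SD 35, site SD 10):
- True ratio 1, 2 to 10 subjects per arm and site: the verdict differed in 1.4% of trials.
- True ratio 1, 150 per arm over sites of 2 to 30 per arm: 1.6%, with limits moving by 0.003 to 0.004 on average.
- True ratio 0.89, same site sizes: 4.3%, with the lower limit moving by 0.006 on average. Overall success rates were 48% and 49%.

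**The case for a change.** The strongest reply is that the rescue rests on a software convention that neither document states. The printed coefficients do not by themselves form an estimable contrast, and a programmer using software that fills with zeros would get no interval. Moreover, site weights cancel in a difference of means but not in a ratio, and the visible text nowhere says how sites are weighted.

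The facts in this reply are right. They do not carry the conclusion, for three reasons. First, the SAP names its software: the code is PROC GLM, so that procedure's rule applies, and zero-filling has no support in the documents. Second, even without the code, the text determines the type of interval, the confidence level, the quantity and the model, so an interval can be obtained from the plan. Third, the open choice of weights has little effect: the two natural choices disagree in about 1% to 4% of simulated trials, and overall success rates hardly change. The redacted sentence in SAP 5.5.1 may also cover this point.

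**Conclusion.** The concern does not hold. The statement, run in the procedure for which it is written, gives the least-squares-mean contrast averaged equally over sites, and the search over c returns the Fieller 90% interval that the SAP and protocol describe. It is neither non-estimable nor a one-site ratio. Spelling out the site coefficients would make the code easier to read but would change no result.

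This rests on PROC GLM's handling of an unlisted CLASS effect, which is known software behaviour but was not run in SAS here. It rests independently on the text, which fixes the interval apart from the site weights. The site numbers, means and SDs in the checks are assumptions. The estimability result and the agreement with Fieller's formula follow from the algebra and do not depend on those values, whereas the 1% to 4% figure does.
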